For the comparison of the study sub-cohorts exposed to anifrolumab and unexposed to anifrolumab within the study cohorts, the RRs will be estimated. The RRs will be estimated if there is at least one event of the relevant outcome observed per exposure group. Both crude and adjusted RRs, with associated 95% CIs, will be estimated for the study outcomes of MCM (objective 2), select pregnancy loss outcomes (composite of spontaneous abortion and stillbirth) (objective 4 & 14), mCM (objective 7), adverse pregnancy outcomes (objective 9), adverse birth outcomes (objective 11). The crude RRs will be estimated before PS adjustment, and the adjusted RRs will be estimated after PS adjustment. If covariate balance is not achieved through PS adjustment, additional adjustment by using unbalanced covariates in the outcome regression model (log-binomial or robust, modified Poisson) will be considered. Additionally, any other potential covariates (or risk factors) that are not included into the PS model but are hypothesised to be associated with the study outcomes may be used as covariates for the statistical models.

The meta-analysis for the primary objectives will be performed using effect size estimates from all study countries for which the adjusted RRs will be estimated. Results of the meta-analysis will be derived using a fixed-effect model since the true effect is expected to be the same in all study countries. Prior to conducting the meta-analyses, heterogeneity across the study countries will be assessed. Considerable heterogeneity would indicate that the study results should be interpreted as inconclusive. Data source-specific results and the overall combined estimate will be presented in forest plots including effect size and 95% CI for each study country included in the analysis.

Milestones

A progress report is planned 12 months after Pharmacovigilance Risk Assessment Committee (PRAC) endorsement of protocol (currently assumed to be Q4 2023). It will contain a status update of database applications and any relevant amendments pertaining to database applications.

Two interim reports will be submitted 36 and 72 months after the progress report.

Interim report 1 will contain descriptive analyses relevant to primary and secondary objectives, for data sources where relevant data is available for reporting. Descriptive analysis conducted in interim report 1 will be blinded to exposure. Interim report 2 will include all descriptive and comparative analyses using all available data at the time of reporting. Exploratory analyses, sensitivity analyses and meta-analyses will not be included in interim report 2.

The final study report is planned for 31 March 2032 and will include all descriptive, comparative, exploratory, sensitivity, and meta-analytic analyses for all data sources from all available data at that time.

- Protocol PRAC approval: Planned date 14 December 2023¹
- Registration EU PASS: Planned date 31 March 2024 (after PRAC endorsement of protocol and before data extraction)
- Progress report: Planned date 31 December 2024
- Anticipated date of first data extraction: Planned date 31 May 2025
- Interim report 1: Planned date 31 December 2027
- Interim report 2: Planned date 31 December 2030
- Last data extraction: Planned date 31 March 2031
- Final report of study results: Planned date 31 March 2032 (15 months after Interim report 2)

¹ This date is an assumption of PRAC approval of the protocol. All subsequent dates are dependent on the actual date of protocol approval by PRAC.

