Since this is a non-interventional observational study, minimal inclusion and exclusion criteria are desirable to minimise potential selection bias and represent real world clinical practice.

Variables

Exposure

The exposure of interest is anifrolumab, irrespective of administration route. *In utero* exposure to anifrolumab (as an add-on therapy to SLE SOC, hereafter referred to as polytherapy) will be compared to non-exposure to anifrolumab (exposed to only SLE SOC).

Exposure to SLE SOC (with the exclusion of anifrolumab) will be assessed from conception (defined as LMP2), until end of first trimester for the outcome of MCM, and from LMP2 until end of pregnancy for all other outcomes, under the assumption that once treatment is started, it continues throughout pregnancy (throughout the first trimester for the outcome of MCM). A look back period of 5-half-lives of the relevant drugs will be considered. This is to account for

prescriptions/dispensations/administrations prior to LMP2 that could lead to *in utero* exposure of the offspring.

Exposure to anifrolumab will be assessed from LMP2 until end of the first trimester for the outcome of MCM, and from LMP2 until end of pregnancy for all other outcomes, or until censoring. Considering the window of clearance of anifrolumab (16 weeks), all patients who receive prescriptions/dispensations/administrations of anifrolumab in the 16 weeks prior to LMP2 or during the first trimester of pregnancy will be considered exposed in the first trimester for the MCM outcome. Patients who receive prescriptions/dispensations/administrations of anifrolumab in the 16 weeks prior to LMP2 or anytime during pregnancy will be considered exposed for all other outcomes.

Offspring whose mother had no anifrolumab prescription/dispensations/administration in the 16 weeks prior to LMP2 or during the first trimester for the outcome of MCM, or during pregnancy for all other outcomes, will be considered unexposed.

Pregnancies exposed to confirmed teratogenic drugs prior to LMP2 until end of first trimester (for MCM outcome) or end of pregnancy (all other pregnancy outcomes), with a look back period of 5-half-lives of the relevant drug, in both the exposed and unexposed groups, will be excluded.

Outcomes

Primary outcomes

The primary outcomes of interest are MCM (defined as a composite of all major MCMs) occurring in live or non-live offspring and select pregnancy loss outcomes (composite of spontaneous abortion and stillbirth).

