From the total number of SLE pregnancies, **the number of anifrolumab exposed pregnancies** in moderate-to-severe SLE women that would be eligible for the study was estimated using the following assumptions: 50% SLE pregnancies occur in women with moderate-to-severe SLE; 80% of SLE pregnancies are unexposed to confirmed teratogenic drugs; 80% of all anifrolumab exposed pregnancies are exposed to anifrolumab during the first trimester of pregnancy; varying anifrolumab exposure of 5% and 10% among pregnant SLE women. Under an assumption of 10% anifrolumab exposed SLE pregnancies and a final study report milestone submission date of 2032, the expected number of anifrolumab exposed pregnancies in the selected data sources which would be eligible for analysis is **353** (USA-Carelon Research 102, USA-DAPI 114, Denmark 8, Finland 6, France 116, Germany 7) **for the MCM outcome** and **497** (USA-Carelon Research 163, USA-DAPI 162, Denmark 11, Finland 7, France 145, Germany 9) **for the select pregnancy loss outcome**.

Given the estimated number of anifrolumab exposed pregnancies in moderate-to-severe SLE women, the **expected number of events for the primary objectives** to be observed were estimated using a prevalence of 7% for MCM and a prevalence of 20% for select pregnancy loss.

Only the data sources where at least one primary outcome (MCM or select pregnancy loss outcomes (composite of spontaneous abortion and stillbirth)) event is expected to be observed will

be considered for the meta-analysis. Under the assumptions of 10% anifrolumab exposed SLE pregnancies and a final study report milestone of 2032, USA-Carelon Research, USA-DAPI, and France will contribute to the meta-analysis for MCM. USA-Carelon Research, USA-DAPI, France, and Denmark will contribute to the meta-analysis for the select pregnancy loss outcome.

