For the select pregnancy loss outcomes, the **index date/start of follow-up**, will be defined as the LMP2 (as defined in Section 9.1) from which the pregnancy will be followed until the outcome of interest. The **exit date/end of follow-up**¹¹ will be defined as the end of the study period, death, emigration (where available), loss to follow-up (disenrollment/de-registering), or date of first diagnosis of the outcome at study, or delivery, whichever is the earliest.

The select pregnancy loss outcomes will be defined as the presence of at least one of the following criteria:

- ICD-10 code of spontaneous abortion¹² (unintended loss of an intrauterine pregnancy) which is less than 22 weeks of gestation for the European data sources (40); less than 20 weeks for the USA data sources (64);
- ICD-10 code of stillbirth¹³ (unintended foetal death occurring at or after 22 weeks of gestation for the European data sources (78); at or after 20 weeks for the USA data sources (64).

Secondary outcomes

During the outcome ascertainment period, outcome events will be identified based on ICD-10 CM codes for the USA, ICD-10 for Denmark, Finland and France; MedDRA codes for Germany recorded in patient registries.

Minor congenital malformations

For this outcome the **index date/start of follow-up**, will be defined as the LMP2 (as defined in Section 9.1) from which the foetus/offspring will be followed up for the outcome of interest. The **exit date/end of follow-up** will be defined as the end of the study period, death, emigration (where available), loss to follow-up (disenrollment/de-registering), reaching the age of 1 year or date of first diagnosis of the outcome at study, whichever is the soonest.

¹¹ Specific outcome censoring rules will be applied. For spontaneous abortion outcome specific end of follow-up will be 22 weeks of gestation for the European data sources or 20 weeks for the USA data sources further details will be specified in the SAP.

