9.5.1.1 Assumptions used for the sample size and power calculations

To estimate the number of anifrolumab exposed SLE pregnancies and the expected number of primary study outcome events in data sources that would be eligible for the analysis in this study, the following assumptions were used:

- **A prevalence of 7% for MCM outcome.** Prevalence of MCM in pregnancies in women with moderate-to-severe SLE was estimated based on a literature search. Among moderate/severe SLE patients exposed to belimumab, birth defect prevalence estimates of 5.6% to 21.7% were observed in post hoc summary of clinical studies and a prospective

pregnancy registry, respectively (86) A prevalence of 6.4% of congenital malformations was observed in renal SLE pregnancies (51) These proxy estimates of MCM in moderate-to-severe SLE align with the observed population based prevalence estimates ranging from 7.4% to 13.6% (114) among women diagnosed with SLE (117).

- **A prevalence of 20% for the composite of select pregnancy loss outcomes (composite of spontaneous abortion and stillbirth).** Prevalence of the composite outcome of select pregnancy loss (spontaneous abortion and stillbirth) in moderate-to-severe SLE pregnancies ranged from 15.3% to 30% (51, 81, 86). For the individual outcomes, the prevalence estimates ranged from 1.8% to 3.7% for stillbirths (51, 103, 120), and the prevalence estimate was 16% (12.1% to 19.9%) for spontaneous abortions (103). Based on the intended objective to evaluate embryo-foetal loss, a composite outcome of spontaneous abortion and stillbirth has been used.
- **Proportion of SLE pregnancies occurring in women with moderate-to-severe disease of 50%.** There is limited information on the proportion of SLE pregnancies that occur in women with moderate-to-severe disease. The proportion of moderate-to-severe disease at the time of diagnosis among the general SLE population is estimated to be 50% (66, 80). Literature regarding medication patterns for SLE pregnant women suggests that 40-45% use immunosuppressors and/or biologics, which may be a proxy indicator of moderate/severe disease (12, 67). Thus, in this study, an assumption of 50% was used.

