- **Proportion of unexposed to confirmed teratogenic SLE SOC and/or non-SLE SOC drugs of 80%.** It is estimated that 80% of the SLE pregnancies are not exposed to SLE SOC and non-SLE SOC confirmed teratogenic drugs before conception, with a time period of 5-half-lives of relevant drug (see list of confirmed teratogenic drugs and half-lives in Table 20), or during pregnancy. This estimate is based on the reported use of SLE SOC and/or non-SLE SOC drugs in SLE population (47, 48).
- **Proportion of anifrolumab exposure during the first trimester of pregnancy of 80%.** The majority of the anifrolumab exposed pregnancies are expected to be unplanned and exposed to anifrolumab only in the early stages of the pregnancy, as the current recommendations indicate that anifrolumab should only be used during pregnancy if the benefit outweighs the risk to the foetus (86). We therefore used the assumption that 80% of all anifrolumab exposed pregnancies are exposed to anifrolumab during the first trimester of pregnancy.
- **Proportion of anifrolumab exposed pregnancies in women with moderate-to-severe SLE of 5% and 10%.** Based on market forecasts, uptake of anifrolumab in the general SLE population is expected to grow from 5% within two years of market launch to 20% by 5 years after market launch. Given the uncertainty of how these forecasts apply to SLE women of child-bearing potential and to use in pregnant SLE women, we used a conservative lower bound (5%) and a more realistic midpoint value (10%) for the proportion of pregnancies in women with moderate-to-severe SLE exposed to anifrolumab.

In addition, to estimate the minimum required sample size and the expected power, the following assumptions were used:

- **Non-inferiority margin of RR of 2.5.** The RR of 2.5 was based on previously reported increase in risk of MCM for exposure to a major teratogenic drug (62).

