as described in Section 9.7.1. In addition, meta-analysis on the data source specific crude and adjusted RRs of MCM in live and non-live offspring from mothers who were exposed or unexposed to anifrolumab during pregnancy will be conducted as described in Section 9.7.1.

Objective 3

The analysis to describe and estimate the risk of select pregnancy loss outcomes (composite of spontaneous abortion and stillbirth) in all pregnancies from the mothers who had moderate/severe SLE and were exposed or unexposed to anifrolumab during pregnancy (study objective 3) will be performed using the *pregnancy* cohort (as defined in Section 9.2.2). The crude and adjusted cumulative incidence (with corresponding 95% CI) of the select pregnancy loss outcomes (composite of spontaneous abortion and stillbirth) will be estimated for cases where mother was exposed to anifrolumab during pregnancy and for cases where mother was unexposed to anifrolumab during pregnancy. The crude cumulative incidence (i.e., risk) will be calculated as the total number of select pregnancy loss outcomes (composite of spontaneous abortion and stillbirth) divided by the total number of pregnancies. The adjusted cumulative incidence (i.e., risk) will be estimated following PS adjustment, if suitable for the data.

Objective 4

To estimate the relative risk of select pregnancy loss outcomes (composite of spontaneous abortion and stillbirth) in pregnancies from the mothers who had moderate/severe SLE and were exposed or unexposed to anifrolumab during pregnancy (study objective 4), the crude and adjusted RR (with corresponding 95% CI) will be estimated using the *pregnancy* cohort (as defined in Section 9.2.2). The crude RR and its 95% CI will be estimated using a regression model as specified in Section 9.7.1. The adjusted RR and its 95% CI will be estimated using the same regression model following an appropriate PS adjustment method as described in Section 9.7.1.

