- Misclassification may occur in the derivation of date of conception. When based on LMP, the derivation of date of conception assumes an average cycle length of 28 days and that conception occurred mid-cycle. The LMP is also subject to accuracy of recall by the woman, regularity of her cycles, and variations in the interval between bleeding and anovulation. When based on gestational age, the degree of misclassification depends on the method and accuracy of the gestational age assessment. However, the misclassification is expected to be within a range of days for most patients.

- Immortal time bias cannot be ruled out. Immortal time is the period during which the outcome of interest cannot occur because of the study design (108). In this study, there is an immortal time because a pregnancy must “survive” until initiation of treatment to be considered as exposed. Nevertheless, it is expected that most pregnant women would have exposure to anifrolumab in the first trimester, and exposure to anifrolumab initiation in the second or third trimester is not expected to be frequent. Adding to this, most outcomes that terminate a pregnancy, such as a spontaneous abortion or an ectopic pregnancy, are expected to happen in the first trimester, thus minimising the impact of this bias.
- The probability of receiving anifrolumab may be related to the length of pregnancy, to some extent. The patients with longer pregnancies have more opportunity (i.e., time) to be prescribed anifrolumab, while the patients with shorter pregnancies have less opportunity (i.e., time) to be prescribed anifrolumab. This may cause a bias in the analysis as shorter pregnancies are more likely to be included in the study cohort unexposed to anifrolumab.
- Both maternal and paternal disease history can be important predictors of the risk of adverse pregnancy outcomes because of shared environmental and genetic risk factors. For this study, no paternal data will be available because linkage to paternal data is not possible for most data sources. Therefore, offspring whose fathers have a history of CM before pregnancy will not be excluded, and no adjustments can be made for potential confounders related to fathers.

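### The primary pregnancy-loss comparison classes exposure over the whole pregnancy but counts risk from LMP2, so late starters contribute immortal time and pull the RR down

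*Protocol*

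**What the plan says.** Exposure (Abstract, Exposure; the same rule in 9.3.1 and Table 5): for every outcome except MCM, a woman with an anifrolumab record "in the 16 weeks prior to LMP2 or anytime during pregnancy will be considered exposed for all other outcomes". This is one ever/never label set from the whole pregnancy.

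Follow-up (9.3.2, select pregnancy loss): the index date is LMP2, "from which the pregnancy will be followed until the outcome of interest", whatever the date of the first dose.

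Risk (9.7.2, Objective 3): the "total number of select pregnancy loss outcomes (composite of spontaneous abortion and stillbirth) divided by the total number of pregnancies". There is no delayed entry and no time-varying exposure.

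Timing of exposure (9.5.1.1): the plan assumes that "80% of all anifrolumab exposed pregnancies are exposed to anifrolumab during the first trimester of pregnancy". Doses in the 16 weeks before LMP2 already count as first-trimester exposure, so the remaining 20% are first exposed later.

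Limitations (9.9): immortal time is acknowledged. It is then played down on two grounds: "exposure to anifrolumab initiation in the second or third trimester is not expected to be frequent", and most pregnancy-ending outcomes occur in the first trimester. Section 9.9 also says that shorter pregnancies are more likely to end up in the unexposed group.

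**The concern.** The label uses information that arises after follow-up has started. A pregnancy first dosed in trimester 2 or 3 must have survived trimester 1, yet that loss-free time is credited to anifrolumab.

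Neither reassurance in 9.9 works. An expectation that late initiation is infrequent sits badly with a planning share of 20%. Early timing of losses enlarges the deficit among late starters instead of shrinking it, because more of the risk lies in the period they have already survived.

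The direction matters. The study aims to rule out an RR of 2.5, and embryo-foetal loss is the non-clinical finding cited in 7.4 as background to the study. A downward bias makes it easier to rule out the margin wrongly.

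**Working it through.** **Inputs from the protocol.** Loss risk R = 0.20 ("a prevalence of 20% for select pregnancy loss"). Share of exposed pregnancies first exposed after trimester 1, s = 1 - 0.80 = 0.20 (9.5.1.1). The plan uses this 80% itself: France falls from 145 exposed for loss to 116 for MCM (9.5.1.2), and 116/145 = 0.80. Margin 2.5, one-sided alpha 2.5%, true RR 1.0 in planning. In the 10% scenario the four sources that enter the loss meta-analysis have 163 + 162 + 11 + 145 = 481 exposed.

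**Assumed input.** Share of losses falling in trimester 1, f = 0.5 to 0.9. The protocol says only that most are early.

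**The plan's own figure first.** Simulating the method of 9.5.1.3 (25/25/22 exposed, 1:2, 20% loss in both groups, inverse-variance pooling, upper 95% bound below 2.5) gives 81.7% power at 72 exposed, against the stated 80%. At 1:3, 61 exposed gives 79.1%. At the expected numbers power exceeds 99%. The stated sizes are reproduced; they assume an unbiased RR.

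**Bias at a true RR of 1.**
- Late-starter risk = R(1 - f)/(1 - Rf)
- Exposed risk = (1 - s)R + s × late-starter risk
- Expected RR = exposed risk / R

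At f = 0.8, late-starter risk = 0.04/0.84 = 4.8%. Exposed risk = 0.8 × 0.20 + 0.2 × 0.048 = 17.0%. Expected RR = 0.170/0.20 = 0.85.

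| f (assumed) | Late-starter risk | Exposed risk | Expected RR |
|---|---|---|---|
| 0.5 | 11.1% | 18.2% | 0.91 |
| 0.6 | 9.1% | 17.8% | 0.89 |
| 0.7 | 7.0% | 17.4% | 0.87 |
| 0.8 | 4.8% | 17.0% | 0.85 |
| 0.9 | 2.4% | 16.5% | 0.82 |

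**Smaller late-starter share (f = 0.8).** s = 0.05 gives 0.96; s = 0.10 gives 0.92.

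**Comparators that also qualify late (f = 0.8, s = 0.20).** If a share c of comparators first has standard-of-care exposure after trimester 1, the denominator becomes (1 - c) × 0.20 + c × 0.048. At c = 0.05 the RR is 0.1695/0.1924 = 0.88. At c = 0.10 it is 0.1695/0.1848 = 0.92. The bias cancels only at c = 0.20.

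**Effect on the rule-out.** At a true RR of 2.5 (f = 0.8, s = 0.20, no late-qualifying comparators) the exposed risk is 2.5 × 17.0% = 42.4%, so the expected RR is 2.12. With 481 exposed at 1:2, the chance of wrongly ruling out 2.5 is:

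| Scenario | Poisson SE | Robust-type variance |
|---|---|---|
| No bias | 0.8% | 2.7% |
| s = 0.20, f = 0.8 | 35% | 51% |
| s = 0.20, f = 0.6 | 17% | 29% |
| s = 0.10, f = 0.8 | 8% | 17% |

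**Cost in power of removing late starters.** About 385 of 481 exposed remain in the 10% scenario, and about 189 of 236 in the 5% scenario. Power to rule out 2.5 stays above 99% in both.

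**The case against.** The strongest reply is that the bias is known and partly handled. Section 9.9 names it. Section 9.7.5 plans an analysis in which comparators must have standard-of-care exposure in the same trimester(s) as the exposed pregnancy had anifrolumab, with a trimester 2 and 3 pregnancy as the example. Such comparators have also survived trimester 1. Objectives 13-14 compare trimester-specific exposure groups. This stands as far as it goes: a reader might infer that the bias went unrecognised, and the document does not support that. But the matched analysis is a sensitivity analysis and Objectives 13-14 are exploratory, so the primary estimate stays uncorrected.

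The size is also open to challenge. The 20% is the complement of a rounded planning value, and 9.5.1.1 expects most exposed pregnancies to be unplanned and exposed only early. Section 9.9 notes that losses in the first 6 weeks are often unrecorded, which would lower the recorded first-trimester share. Comparators must have standard-of-care exposure during pregnancy (with a 5-half-life look-back), so some may also qualify late. All three points stand. They are why the range runs up to 0.96; none reverses the direction unless late qualification is as common among comparators as among the exposed.

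Two stronger readings are tempting.
- A reader might infer that elective termination is nowhere treated as ending follow-up. It is missing from the exit list for this outcome in 9.3.2, but note i to Figure 2 ends follow-up there, 9.3.1 calls it a censoring event, and the footnote in 9.3.2 leaves outcome-specific censoring rules to the SAP. Because risk is "divided by the total number of pregnancies", censoring does not enter the planned estimate anyway.
- A reader might infer that preterm birth (Objectives 10-11) is distorted in the same way. Those objectives include live births only, so both groups have survived trimester 1. The issue there is mainly third-trimester starters, and it is not quantified here.

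**Conclusion.** The point holds for the primary pregnancy-loss comparison. Ever/never exposure, follow-up from LMP2 and a simple proportion together bias the RR downward, the grounds in 9.9 for discounting this are unsound, and no planned analysis repairs the primary estimate.

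Under the plan's 20% loss and 20% late starters, with no late-qualifying comparators, a true RR of 1.00 is expected as about 0.91 to 0.82 for 50-90% of losses in trimester 1. With 5-10% late starters, or 5-10% late-qualifying comparators, it is about 0.88-0.96 (at 80% early losses). The first-trimester share is an assumption, and the 20% is a planning value, not data. The false rule-out figures depend on the same inputs and assume no late-qualifying comparators. The stated sample size and power are not in dispute.

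**What to change.** In the primary analysis for Objectives 3-4:
- Start each exposed pregnancy at its first exposure, or at LMP2 if dosed in the prior 16 weeks.
- Match on the propensity score to standard-of-care pregnancies still ongoing and anifrolumab-free at the same gestational week, or trimester where dating is coarse, with standard-of-care status judged by that time.
- Count losses from that time in both groups.

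Alternatives are to restrict the primary contrast to exposure at or before LMP2 (with the 16-week look-back), or to use a trimester landmark. Merely dropping pregnancies first exposed after trimester 1 would leave the smaller immortal time of first doses within trimester 1.

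Keep the ever-exposed analysis as a sensitivity analysis. Correct the reasoning in 9.9. Add elective termination to the exit list in 9.3.2 so that it agrees with Figure 2 and 9.3.1.

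Cost: protocol and SAP wording and more matching code, with no new data source. Some exposed pregnancies may go unmatched. Alignment would rest on estimated dates for many losses: 9.3.3 says gestational age is rarely available for miscarriages, and the notes to Table 17 say that Carelon assigns a fixed value when no code exists. Week or trimester alignment is therefore more realistic than exact-day matching. Power is not an obstacle.
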